12.1.2 Hypothesis Testing

Primary hypothesis testing on the odds ratio: The null hypothesis is that the vIGA-AD success does not differ between roflumilast cream 0.15% and matching vehicle cream. The alternative hypothesis is that the vIGA-AD success does differ between roflumilast cream 0.15% and matching vehicle cream.

Null Hypothesis (H_0): $P_R Q_V / P_V Q_R = 1.0$,

Alternative Hypothesis (H_A): $P_R Q_V / P_V Q_R \neq 1.0$, where

P_R = the proportion of vIGA-AD success in roflumilast cream 0.15%

P_V = the proportion of vIGA-AD success in matching vehicle cream

$Q_R = 1 - P_R$

$Q_V = 1 - P_V$.

12.1.3 Primary Endpoint Analysis

For the primary analysis, missing vIGA-AD scores will be imputed using multiple imputation as described in Section 6.2.1. These imputations will result in a minimum of 25 to a maximum of 250 complete analysis datasets, depending on the number of imputed monotone datasets that are required.

Percentages of subjects having a vIGA-AD Success (refer to Section 12.1.1) will be presented by visit and treatment group based on multiply imputed data in the ITT population along with a 95% Wilson CI. The common MH odds ratio and common MH proportion difference, adjusted for the randomization factors (i.e., randomized vIGA-AD score and pooled study site) will also be provided along with their common associated 95% CIs. Additionally, count and percentage of subjects having a vIGA-AD success, count and percentage of subjects in each category of the vIGA-AD scale, and descriptive statistics for the vIGA-AD scores, change in vIGA-AD score from

	STATISTICAL ANALYSIS PLAN, Version 3.0
Protocol Number: ARQ-151-311	Sponsor: Arcutis Biotherapeutics, Inc.

baseline and percent change in vIGA-AD score from baseline will be presented by visit and treatment group based on observed data in the ITT population.

The primary endpoint (vIGA-AD Success at Week 4) will then be analyzed using multiple imputation CMH test stratified by the randomization factors. To do so, a CMH analysis will be performed separately for each of the complete multiply imputed analysis data sets, and results will be combined into one multiple imputation inference using the methodology described in Section 6.2.1. Statistical significance will be concluded at the 5% significance level (2-sided). Should the odds ratio be not estimable for at least one multiply imputed dataset, the conclusion of the study will be based on the p-value obtained from a MH test, stratified by the randomization factors, for the common MH proportion difference at Week 4.

The following sensitivity analyses to the primary analysis of the primary endpoint will be performed:

- Multiply-imputed data (refer to Section 6.2.1) on mITT population (refer to Section 4.2) and
- Tipping Point analysis (refer to Section 6.2.3) on ITT population.
- Non-responder imputation (refer to Section 6.2.2) on ITT population.
- Observed data on ITT population (refer to Section 4.1).
- Observed data on PP population (refer to Section 4.3).

For the last three sensitivity analyses, count of subjects having vIGA-AD success will also be presented by visit and treatment group in addition to the percentage of subjects having vIGA-AD success.

To assess the impact of the pooling of the study sites on the primary analysis of the primary endpoint, the following analyses will be performed:

- The primary analysis of the primary efficacy endpoint will be repeated but with a different site pooling strategy (refer to Section 6.4).
- To assess the impact of site on the primary analysis endpoint, the proportion of subjects achieving vIGA-AD success and 95% CI within each site will be tabulated. No p-values will be provided. Forest plots of the proportions (and associated 95% CI) for each site and treatment will also be provided.

	STATISTICAL ANALYSIS PLAN, Version 3.0
Protocol Number: ARQ-151-311	Sponsor: Arcutis Biotherapeutics, Inc.

- An additional analysis to examine the impact of study site will examine the changes in p-values that occur after removal of subjects from a site. To do so, the primary analysis of the primary efficacy endpoint will be repeated but removing a different pooled study site for each iteration. Forest plots of the odds ratio (and associated 95% CI) for each pooled site removed will also be provided.

12.2 Secondary Endpoints Analysis

Secondary efficacy endpoints are based on the vIGA-AD scale, WI-NRS scale or EASI questionnaire. The list of secondary efficacy endpoints can be found in Section 2 and their derivation in Section 5.5.

- For more details about the vIGA-AD scale refers to Section 12.1.1.
- The WI-NRS scale is a single item scale assessing the subject-reported worst itch severity during the previous 24-hour period. The scale is from 0 to 10 ('no itch' to 'worst itch imaginable').
- For the EASI questionnaire, four anatomic sites (head, upper extremities, trunk, and lower extremities) are assessed for erythema, induration/infiltration (papules), excoriation, and lichenification as seen on the day of the examination. The severity of each sign is assessed using a 4-point scale (half steps are allowed e.g., 0.5): 0 (none), 1 (mild), 2 (moderate), and 3 (severe). The area affected by AD within a given anatomic site is estimated as a percentage of the total area of that anatomic site and assigned a numerical value according to the degree of AD involvement as follows: 0 (no involvement), 1 (1-9%), 2 (10-29%), 3 (30-49%), 4 (50-69%), 5 (70-89%), and 6 (90-100%).

For each secondary efficacy endpoint, missing data will be imputed and data will be summarized as for the primary efficacy endpoint (refer to Section 12.1.3).

Upon successful demonstration of statistical significance for the primary efficacy endpoint, the secondary efficacy endpoint of vIGA-AD success among subjects with vIGA-AD score of 'Moderate' at randomization will be analyzed as described for the primary efficacy endpoint (refer to Section 12.1.3) but based on the vIGA-AD Moderate ITT population (refer to Section 4.4) and stratifying by pooled study site only. That is, as per the vIGA-AD Moderate ITT population definition all subjects included in this analysis will have a randomized vIGA-AD score of Moderate (3) and so, the CMH test cannot be stratified by randomized vIGA-AD score.

Upon successful demonstration of statistical significance for the primary and above secondary efficacy endpoints, the remaining secondary efficacy endpoints will be grouped into secondary

	STATISTICAL ANALYSIS PLAN, Version 3.0
Protocol Number: ARQ-151-311	Sponsor: Arcutis Biotherapeutics, Inc.

endpoint family 1, comprised of the 4-point reduction on the average weekly WI-NRS at Week 4, Week 2 and Week 1, and secondary endpoint family 2, comprised of the EASI-75 at Week 4, vIGA-AD of ‘clear’ or ‘almost clear’ at Week 4, vIGA-AD of success at week 2 and week 1, vIGA-AD of ‘clear’ or ‘almost clear’ at Week 2 and Week 1. The analysis of secondary endpoint family 1 will be performed as described for the primary efficacy endpoint (refer to Section 12.1.3) but based on the WI-NRS population (refer to Section 4.6) and an alpha level of 0.03 will be used to test these endpoints sequentially as described in Section 6.5. Similarly, the analysis of secondary endpoint family 2 will be performed as described for the primary efficacy endpoint (refer to Section 6.2.1) based on the ITT population (refer to Section 4.1) but an alpha level of 0.02 will be used to test these endpoints sequentially as described in Section 6.5.

Secondary Endpoint Family 1 ($\alpha=0.03$, hierarchical testing)

- In subjects ≥ 12 years old with baseline WI-NRS ≥ 4 , achievement of at least a 4-point reduction in the average weekly WI-NRS at Week 4
- In subjects ≥ 12 years old with baseline WI-NRS ≥ 4 , achievement of at least a 4-point reduction in the average weekly WI-NRS at Week 2
- In subjects ≥ 12 years old with baseline WI-NRS ≥ 4 , achievement of at least a 4-point reduction in the average weekly WI-NRS at Week 1

Secondary Endpoint Family 2 ($\alpha = 0.02$, hierarchical testing)

- Achievement of at least a 75% reduction in the Eczema Area and Severity Index at Week 4 (EASI-75)
- vIGA-AD of ‘clear’ or ‘almost clear’ at Week 4
- vIGA-AD Success at Week 2
- vIGA-AD Success at Week 1
- vIGA-AD of ‘clear’ or ‘almost clear’ at Week 2
- vIGA-AD of ‘clear’ or ‘almost clear’ at Week 1

For the secondary efficacy endpoint of vIGA-AD Success at Week 4 based on the vIGA-AD moderate ITT population, the following sensitivity analyses to the primary analysis of this efficacy endpoint will be performed if and only if the hierarchical testing procedure (refer to Section 6.5) allows it:

- Tipping Point analysis (refer to Section 6.2.3) on vIGA-AD moderate ITT population.

	STATISTICAL ANALYSIS PLAN, Version 3.0
Protocol Number: ARQ-151-311	Sponsor: Arcutis Biotherapeutics, Inc.

- Non-responder imputation (refer to Section [6.2.2](#)) on vIGA-AD moderate ITT population.
- Observed data on vIGA-AD moderate ITT population.
- Observed data on vIGA-AD moderate PP population (refer to Section [4.5](#)).

For the last three sensitivity analyses, count of subjects having vIGA-AD success will also be presented at Week 4 by treatment group in addition to the percentage of subjects having vIGA-AD success.

For all other secondary efficacy endpoints, the following sensitivity analyses to the primary analysis of these secondary endpoints will be performed if and only if the hierarchical testing procedure (refer to Section [6.5](#)) allows it:

- Non-responder imputation on WI-NRS population for the WI-NRS secondary efficacy endpoints and ITT population for all other secondary efficacy endpoints.
- Observed data on WI-NRS population for the WI-NRS secondary efficacy endpoints and ITT population for all other secondary efficacy endpoints.

The daily WI-NRS score, average weekly WI-NRS, and WI-NRS success flag will be listed.

The EASI total score and EASI-75 flag at each visit will be listed.

12.3 Exploratory Efficacy Endpoints

Exploratory efficacy endpoints are based on the vIGA-AD scale, WI-NRS scale, EASI questionnaire, %BSA affected by AD, CDLQI/DLQI questionnaires, DFI questionnaire, SCORAD tool or POEM tool. The list of exploratory efficacy endpoints can be found in Section [2](#) and their derivation in Section [5.5](#).

- For more details about the vIGA-AD scale, refer to Sections [12.1.1](#).
- For more details about the WI-NRS scale, refer to Section [12.2](#).
- For more details about the EASI questionnaire, refer to Section [12.2](#).
- The % of BSA affected by AD will be determined by the subject's hand method, where the subject's hand (including fingers) surface area is assumed to equal 1% of BSA (excluding the scalp, palms, and soles).
- The CDLQI/DLQI is a self-administered validated questionnaire designed to measure the health-related quality of life of children/adult subjects suffering from a skin disease. It

	STATISTICAL ANALYSIS PLAN, Version 3.0
Protocol Number: ARQ-151-311	Sponsor: Arcutis Biotherapeutics, Inc.

consists of 10 questions concerning subjects' perception of the impact of skin disease on different aspects of their health-related quality of life over the last week. Questions 1 to 6 and 8 to 10 are rated from 0 (Not at all) to 3 (Very much). For children, if last week was a school time, question 7 is rated from 0 (Not at all) to (Prevented school) but if the last week was a holiday time, question 7 is rated from 0 (Not at all) to 3 (Very much). For adults, question 7 is rated from 0 (Not at all/Not relevant/No) to 3 (Yes).

- The DFI questionnaire measures how much having a child with AD affects the quality of life of other (adult) members of the family over the last week. It is designed to be completed by caregivers of subjects \leq 17 years of age and consists of 10 questions rated from 0 (Not at all) to 3 (Very much).
- The SCORAD is a clinical tool to assess the severity (i.e., extent, intensity) of AD as objectively as possible. First, the overall %BSA affected by AD is evaluated (from 0% to 100%, where a subject's palm represents 1% of his/her total BSA). Secondly, the AD severity is evaluated based on 6 items (erythema, edema/papulation, oozing/crusts, excoriation, lichenification, and dryness) graded using a 4-point scale (half steps are not allowed): 0 (absence), 1 (mild), 2 (moderate), and 3 (severe). Lastly, 2 subjective items (loss of sleep and intensity of pruritus) are evaluated by having the subject indicates on a 10.0 cm visual analog scale (VAS) the point corresponding to the average value over the last 3 days (0 cm = none to 10 cm= maximum).
- The POEM is a tool used for monitoring atopic eczema severity. It focuses on the illness as experienced by the subject. It consists of a 5-point scale measuring the frequency of each of 7 AD symptoms (i.e., dryness, itching, flaking, cracking, sleep loss, bleeding, and weeping) over the past week scored from 0 (no days), 1 (1 to 2 days), 2 (3 to 4 days), 3 (5 to 6 days), and 4 (every day).

For the continuous exploratory efficacy endpoints of change and percent from baseline in average weekly WI-NRS, EASI total score, % BSA, DLQI/CDLQI score, DFI score, SCORAD score, and POEM score at Week 1, Week 2, and Week 4, descriptive statistics for the score, change from baseline and percent change from baseline will be presented by visit and treatment group based on observed data in the ITT population. Descriptive statistics will also be presented similarly for the average weekly WI-NRS at Week 3. For the continuous efficacy exploratory endpoint of daily WI-NRS, descriptive statistics will be presented similarly but on a daily basis instead of a weekly basis. Additionally, a plot of the mean (and standard error) daily WI-NRS scores over time for each treatment group will also be provided based on observed data. A similar plot will be provided for the percent change from baseline in daily WI-NRS.

	STATISTICAL ANALYSIS PLAN, Version 3.0
Protocol Number: ARQ-151-311	Sponsor: Arcutis Biotherapeutics, Inc.

For each categorical exploratory efficacy endpoint, count and percentages of subjects meeting the criteria for an exploratory efficacy endpoint will be presented by visit and treatment group based on observed data in the ITT population along with a 95% Wilson CI. Additionally, count and percentage of subjects meeting the criteria for vIGA-AD of Clear (0), EASI-50, EASI-90, and EASI-100 at Week 1 and Week 2 will also be presented by visit and treatment group based on observed data in the ITT population along with a 95% Wilson CI.

Continuous exploratory efficacy endpoints will be analyzed at Week 1, Week 2, and Week 4 and for daily WI-NRS assessments using an analysis of covariance (ANCOVA) with the factors of treatment, two stratification variables (pooled study site and randomized vIGA-AD score), and baseline of the variable under analysis as covariate. Statistical comparisons between the treatment groups will be obtained using contrasts. The Least Square (LS) mean and its standard error, difference in LS means between treatment group (i.e., active - vehicle), its standard error and associated 95% confidence interval, and p-value for difference from vehicle will be presented at each visit. These analyses will be performed based on observed data in the ITT population.

Categorical exploratory efficacy endpoints at Weeks 1, 2, and 4 will be analyzed using a CMH test adjusted for the two stratification variables (pooled study site and randomized vIGA-AD score). Common MH odds ratio, common MH proportion difference and their common associated 95% CI, adjusted for the randomization factors, will be provided. The p-value will be from a CMH test for the common MH odds ratio, unless the common MH odds ratio is not estimable. In such circumstances, the p-value will be from a MH test for the common MH proportion difference.

The analysis of these endpoints will be performed on the observed data with no imputation. The p-values will be nominal as no formal inferential testing will be done on exploratory efficacy endpoints.

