2 STUDY OBJECTIVES AND ENDPOINTS

OBJECTIVES	ENDPOINTS
Efficacy	
To assess the efficacy of Roflumilast (also known as ARQ-151) cream 0.15% vs vehicle administered once daily	
Primary efficacy endpoint:
 
 • Validated Investigator Global Assessment scale for Atopic Dermatitis (vIGA-AD) Success, defined as a vIGA-AD score of 'clear' (0) or 'almost clear' (1)

	STATISTICAL ANALYSIS PLAN, Version 3.0
Protocol Number: ARQ-151-311	Sponsor: Arcutis Biotherapeutics, Inc.

OBJECTIVES	ENDPOINTS
(QD) x 4 weeks to individuals 6 years of age and older with atopic dermatitis (AD).	
plus at least a 2-grade improvement from Baseline at Week 4
 
Secondary efficacy endpoints:
 
 • In subjects with a vIGA-AD score of 'Moderate' at randomization, vIGA-AD Success at Week 4 • In subjects ≥ 12 years old with baseline Worst Itch - Numeric Rating Score (WI-NRS) ≥ 4, achievement of at least a 4-point reduction on the WI-NRS at Week 4 • In subjects ≥ 12 years old with baseline WI-NRS ≥ 4, achievement of at least a 4-point reduction on the WI-NRS at Week 2 • In subjects ≥ 12 years old with baseline WI-NRS ≥ 4, achievement of at least a 4-point reduction on the WI-NRS at Week 1 • Achievement of at least a 75% reduction in the Eczema Area and Severity Index (EASI-75) at Week 4 • vIGA-AD of 'clear' or 'almost clear' at Week 4 • vIGA-AD Success at Week 2 • vIGA-AD Success at Week 1 • vIGA-AD of 'clear' or 'almost clear' at Week 2 • vIGA-AD of 'clear' or 'almost clear' at Week 1 
Exploratory efficacy endpoints:
 
 • Other continuous efficacy endpoints include change and percent change in average weekly WI-NRS and daily WI-NRS, EASI, % body surface area (BSA) affected by AD, Dermatology Life Quality Index (CDLQI/DLQI), the Dermatitis Family Impact (DFI), Scoring Atopic Dermatitis (SCORAD), and Patient-oriented Eczema Measure (POEM) at Week 1, Week 2 and Week 4. • Other categorical efficacy endpoints include EASI-50, EASI-90, EASI-100, and vIGA-AD of 'clear' at Week 4
Safety	

	STATISTICAL ANALYSIS PLAN, Version 3.0
Protocol Number: ARQ-151-311	Sponsor: Arcutis Biotherapeutics, Inc.

OBJECTIVES	ENDPOINTS

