4.6 WI-NRS Population

WI-NRS population will be a subset of the ITT population among subjects ≥ 12 years old with average weekly baseline WI-NRS score ≥ 4 .

The subjects in WI-NRS population are those:

1. Completed at least 4 of 7 evaluable daily WI-NRS questionnaires during the last 7 days of the Screening period;
2. Have a mean baseline WI-NRS score ≥ 4.0 , defined as the average of all non-missing scores reported during the last 7 days of the Screening period if at least 4 of 7 evaluable daily WINRS questionnaires available. If 4 or more evaluable daily questionnaires are missing, then the data will be treated as missing.

All subjects will be analyzed according to the treatment group and stratum to which they were randomized.

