- DFI Score = sum of the 10 questions (individual questions scored as Very much=3, A lot=2, A little=1; Not at all=0), ranging from 0 to 30. If 1 item is missing, it is scored as 0 for that item. If 2 or more items are missing, the score should not be calculated.
- PHQ-8 = sum of the 8 questions (individual questions scored as Not at all=0, Several days=1, More than half the days=2, and Nearly every day=3), ranging from 0 to 24. If more than 1 item is missing the score should not be calculated. If 1 item is missing the score is calculated as (sum of answered items*8)/number of answered items (=7).
- Modified PHQ-A = sum of the 8 questions (individual questions scored as Not at all=0, Several days=1, More than half the days=2, and Nearly every day=3), ranging from 0 to 24. If more than 1 item is missing the score should not be calculated. If 1 item is missing, the score is calculated as (sum of answered items*8)/number of answered items (=7).
- CDI-2 total score is a sum of the 17 questions based on the scoring grid (individual questions scored as much or most of the time=0, often=1, some of the time=2, Not at all=3 for questions Q2, Q7, Q13, Q14, and Q16; individual questions scored as much or most of the time=3, often=2, some of the time=1, Not at all=0 for all other questions), ranging from

	STATISTICAL ANALYSIS PLAN, Version 3.0
Protocol Number: ARQ-151-311	Sponsor: Arcutis Biotherapeutics, Inc.

0 to 51. All CDI-2 raw scores can be prorated using the following formula, rounding to the nearest whole number:

- Prorated score = (Obtained raw score for scale) * (Total # of items on scale/subscale) / Total # items on scale/subscale with responses
- CDI-2 emotional problem scale is a sum of 9 questions (Q1, Q3-6, Q8, Q10-12). If more than 1 item is missing the score should not be calculated. If 1 item is missing the score is calculated as (sum of answered items*9)/number of answered items (=8).
- CDI-2 functional problem scale is a sum of 8 questions (Q2, Q7, Q9, Q13-17). If more than 1 item is missing the score should not be calculated. If 1 item is missing the score is calculated as (sum of answered items*8)/number of answered items (=7).

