5.6 Descriptive Statistics

All continuous variables will be summarized by presenting the number of subjects, mean, standard deviation (SD), median, Q1, Q3, minimum, and maximum. For PK endpoints, geometric statistics including geometric mean and coefficient of variation (CV) will also be provided.

Categorical variables will be presented as frequencies and percentages.

Summary tables will be presented by visit, when applicable.

Change from baseline will be calculated as:

	STATISTICAL ANALYSIS PLAN, Version 3.0
Protocol Number: ARQ-151-311	Sponsor: Arcutis Biotherapeutics, Inc.

Assessment value at postbaseline visit X – baseline value.

Percent change from baseline will be calculated as:

$$(\text{Assessment value at postbaseline visit X} - \text{baseline value}) \times 100\% / (\text{baseline value})$$

Percent change from baseline will be missing in situation where baseline value equals to 0.

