13.3 Vital Signs

Descriptive statistics will be presented for vital signs (systolic blood pressure, diastolic blood pressure, heart rate, body temperature, and weight). Observed values, change from baseline and percent change from baseline values will be presented by treatment group at each scheduled visit.

The number and percentage of subjects with gain or lose $>5\%$ from baseline in body weight over the course of the study will be summarized for overall and separately for children and adolescents (6 to 17 years) and adults (≥ 18 years). BMI will be summarized using descriptive statistics (n, mean, standard deviation, median, Q1, Q3, minimum, and maximum) on observed values, change from baseline and percent change from baseline values separately for children and adolescents (6 to 17 years) and adults (≥ 18 years). The BMI percentile rather than BMI kg/m^2 will be summarized for children and adolescents (6 to 17 years).

A listing of all vital sign assessments including weight, BMI, and BMI percentile for children and adolescents will be provided.

	STATISTICAL ANALYSIS PLAN, Version 3.0
Protocol Number: ARQ-151-311	Sponsor: Arcutis Biotherapeutics, Inc.

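### Percent change from baseline is tested on scales with no minimum baseline and summarised for BMI percentile; near-zero baselines can make the estimates unstable, by an amount the documents do not fix

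*SAP*

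**What the plan says.** SAP 2 makes percent change an endpoint, not just a display: "Other continuous efficacy endpoints include change and percent change in average weekly WI-NRS and daily WI-NRS, EASI", followed by %BSA, CDLQI/DLQI, DFI, SCORAD and POEM.

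SAP 12.3 describes the summaries ("For the continuous exploratory efficacy endpoints of change and percent from baseline in average weekly WI-NRS" and the other scales), then the test: "Continuous exploratory efficacy endpoints will be analyzed at Week 1, Week 2, and Week 4 and for daily WI-NRS assessments using an analysis of covariance". The model has treatment, pooled site, randomized vIGA-AD score and the baseline value. It yields LS means, their difference with a 95% confidence interval, and a p-value. On the analysis set: "These analyses will be performed based on observed data in the ITT population". The section also plans a mean and standard error plot of daily WI-NRS, and a similar plot of its percent change.

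The only safeguard is in SAP 5.6: "Percent change from baseline will be missing in situation where baseline value equals to 0". A minimum itch score does exist in SAP 4.6 ("Have a mean baseline WI-NRS score" of at least 4.0), but that population serves the responder endpoints, not this ANCOVA. The entry criteria in the protocol synopsis and Section 4.5.1 set minimums for EASI (about 5) and BSA (3%). They set none for WI-NRS, DLQI/CDLQI, DFI or POEM.

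SAP 13.3 summarises BMI "on observed values, change from baseline and percent change from baseline values separately for children and adolescents" and for adults, and uses BMI percentile in place of kg/m2 at ages 6 to 17. A percent change of a percentile follows.

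**The concern.** Percent change divides by the baseline. On a scale that can start near zero, improvement stops at -100% while worsening can run to several hundred percent. One subject with a tiny baseline can then outweigh many ordinary ones in a mean, an LS mean or a residual variance. Subjects with baseline 0, who can only stay the same or worsen, leave the percent-change analysis but remain in the absolute-change analysis, so the two ANCOVAs describe different subjects.

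For BMI percentile the denominator is itself a nonlinear transform of body size. The same physiological shift looks large in a light child and almost nil in a heavy one. Protocol 2.3.7 records weight loss with oral roflumilast, so the paediatric table should read evenly across the range.

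At stake are the itch percent-change curve, its nominal p-values and those for the quality-of-life and symptom scores, and the readability of one safety table.

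**Working it through.** The plan gives no SD, effect size or power for any percent-change endpoint, so there is no stated figure to reproduce. The check covers the arithmetic, then an illustration on assumed inputs, then the percentiles.

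**1. Arithmetic from the SAP 5.6 formula**, (post - baseline) x 100 / baseline.

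| Baseline | Effect of a 1-point worsening |
|---|---|
| WI-NRS 6 | 1/6 = +17% |
| WI-NRS 1 | 1/1 = +100% |
| WI-NRS 0.5 | 1/0.5 = +200% |
| WI-NRS 1/7 (smallest non-zero mean of seven whole-number daily scores) | 1/(1/7) = +700% |
| EASI 5 (about the entry minimum) | 1/5 = +20% |
| BSA 3% (entry minimum) | 1/3 = +33% |

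A daily itch score going from 1 to 5 is +400%, which offsets eight subjects at -50% (8 x 50 = 400). On a 0-30 scale ("DFI Score = sum of the 10 questions"; DLQI and CDLQI have the same range), the worst change from 1 is (30 - 1)/1 = +2900%. EASI and BSA are protected by their entry minimums; the other scales are not.

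**2. Illustration for weekly WI-NRS.** From the SAP: 650 subjects, 2:1, two-sided 0.05. Assumed, because the documents are silent: baseline mean 5.5 and SD 2.3, reduction 25% on vehicle and 38% on active, noise SD 1.8. The ANCOVA has treatment and baseline only; site and severity strata are omitted.

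| Noise model | Power, percent change, ITT | Power, percent change, baseline >=4 |
|---|---|---|
| Constant, SD 1.8 even near baseline 0 | about 73% | about 99% |
| Proportional to square root of baseline | 98.8% | 99.2% |
| Proportional to baseline | 99.7% | 98.0% |

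Repeat runs of the constant-noise case gave 73% to 77%. In that case only about 2% of subjects had a baseline below 1, yet those at or below 1 carried about 43% of the residual sum of squares, and absolute change in ITT had power near 100%. Still with constant noise, moving the assumed baseline to mean 6 and SD 2 raises percent-change power to 96%.

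**3. Illustration for a 0-30 quality-of-life scale.** With assumed baseline means of 6, 8 and 10 and an assumed moderate effect, power is 68%, 78% and 82% for percent change, and 95%, 99% and 99.5% for absolute change. Type I error with no effect is 0.044 to 0.047 for percent change.

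**4. BMI percentile.** New percentile = Phi(z - 0.2), with z the probit of the old percentile.

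| Start | z | z - 0.2 | New percentile | Percent change | Percentile points |
|---|---|---|---|---|---|
| 3rd | -1.881 | -2.081 | 1.87 | -37.6% | -1.1 |
| 50th | 0 | -0.2 | 42.07 | -15.9% | -7.9 |
| 99th | 2.326 | 2.126 | 98.33 | -0.7% | -0.7 |

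Change in percentile points is uneven too, which is why the z-score is the better scale.

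**The case against.** The strongest reply is that nothing confirmatory depends on this. SAP 12.3 calls the exploratory p-values nominal. The confirmatory itch endpoint is an absolute 4-point reduction in subjects aged 12 and over with baseline at least 4. Absolute change is already tested by the same ANCOVA for every scale, and SAP 5.6 already supplies medians and quartiles in the tables. All of that stands, and it keeps the point small.

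Four stronger readings are tempting, and the documents do not support them.

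- **A few subjects will drive the result.** That needs the baseline distribution and the noise structure, and the plan gives neither. The loss is marked under constant noise, disappears under square-root noise and reverses under proportional noise. The most one can say is that they can.
- **The test produces false positives.** In the simulations the cost was precision; Type I error stayed near 0.05.
- **Itch percent change should be confined to baseline >=4.** Under the same assumed inputs this drops about 25% of subjects and turns an ITT summary into a subgroup. That is a poor trade when absolute change in all subjects is already planned.
- **Paediatric weight loss would be missed.** SAP 13.3 reports weight with change and percent change at each visit, and gains or losses above 5% separately for ages 6-17. SAP 13 repeats the weight-change summary by age group. The schedule footnotes send losses of 5% or more to the medical monitor. The percentile row is a weak display, not the safety monitor.

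**Conclusion.** The point holds as a minor one. For WI-NRS, DLQI/CDLQI, DFI and POEM the plan tests a ratio whose denominator has no minimum above zero, so near-zero baselines can inflate the variance and destabilise the LS means. Whether they will is unknown: for weekly WI-NRS under the assumed means and effects, power for percent change lies anywhere from about 73% to over 99% depending on how noise scales with baseline. The quality-of-life figures rest equally on assumed distributions.

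The BMI percentile result needs no trial data. It is exact under the normal transform: the same 0.2 z fall is shown as anything from -37.6% to -0.7% according to where the child starts.

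The primary and secondary endpoints are unaffected, and EASI and BSA are bounded by their entry minimums.

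**What to change.** **(a) SAP 12.3.** For WI-NRS (weekly and daily), DLQI/CDLQI, DFI and POEM, report ANCOVA LS means, confidence intervals and p-values on absolute change only; that analysis is already planned. Present percent change on these scales, including the daily WI-NRS plot, as median and quartiles. Do not restrict to baseline >=4. State how many subjects are left out of percent change because their baseline is 0.

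**(b) SAP 13.3.** For ages 6-17, replace percent change in BMI percentile with change in BMI z-score, the probit of the percentile already derived under SAP 8, taken before any rounding. Also show BMI in kg/m2.

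**Cost.** SAP wording and small reprogramming before lock. There would be no nominal p-value for percent change on these scales. For DLQI/CDLQI, DFI and POEM, Section 6.14.1 of the supplied protocol asks only for a descriptive analysis of the reduction in total score. The SAP is written to Amendment 4, so its wording should be checked before the change is made.
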